Clinical research will follow the relevant provisions of the Helsinki Declaration of the World Medical Congress. Prior to the commencement of the study, the study shall be approved by the Ethics Committee before it can be implemented. Before each subject enrolls in this study, the researcher has the responsibility to fully and comprehensively introduce the purpose, procedure, and possible risks of the study to the subject or his agent, and to sign a written informed consent form. The patients should know that they have the right to withdraw from the study at any time, and the informed consent should be kept as a clinical research document for reference. In the course of the study, the patient's personal privacy and data confidentiality will be protected.

(2) Examination and approval of the trial scheme

The approval of the clinical trial program is carried out by the ethics committee, and the clinical trial can only be carried out after the final ethical approval has been obtained.

(3) Informed consent process and informed consent form text

Before being enrolled in this study, the researcher must explain the details of the clinical trial to the subject or his guardian, including the trial content, trial purpose, expected efficacy, possible adverse events, and countermeasures. Only after the patients fully understand the experiment and sign the informed consent form can they be selected.

Incapacitated patients can also enter clinical trials if the ethics committee agrees in principle and the researchers believe that it is in their own interest to participate in clinical trials, but their guardians should sign and date them before the trial. Patients

with acute ischemic stroke may not be in a coma clinically, but their cognitive ability and hand function are affected. Such patients should be signed and dated by their guardians before the trial.

When the subject or his guardian is unable to read, there shall be a witness present in the informed process. After a detailed explanation of the informed consent form, the witness reading the informed consent form is consistent with the oral informed content. With the oral consent of the subject or his guardian, the witness shall sign and date the informed consent form, and the signature of the witness shall be on the same day as that of the researcher.

8、Deviation of the clinical trial scheme and provisions for revision of the clinical trial scheme

Before the beginning of clinical verification, the trial scheme is finalized and signed by various researchers after joint discussion and revision, and submitted to the Ethics Committee for approval before implementation.

If there are problems in the actual implementation of the clinical verification, the scheme needs to be revised, and it should be proposed to the implementer that, after multi-center consultation and discussion, the responsible unit shall revise the scheme, submit it in writing to the implementer and each participating research unit for signature and approval, and then submit it to the ethics committee for approval.

In the course of the clinical trial, if the existing clinical trial center fails to pass the examination and approval of the clinical trial management department or the ethics committee, which leads to the trial progress being significantly lower than the expected plan, the organizer shall make adjustments to the participating center (abandon selection or increase) after full communication with the coordinating researcher, but can only update the list of clinical trial institutions in the attachment without amending the text of the plan. The final list of participating clinical trial centers should be

submitted to the clinical trial management departments and ethics committees of all participating units for the record.

If important and new information relating to the experimental group is discovered, the informed consent form must be submitted to the Ethics Committee for approval and the consent of the patients must be obtained again.

If the trial deviates from the trial plan, the researcher must inform the ethics committee in a timely manner.

9、Direct access to source data and files

In this clinical study, the main researchers and their authorized researchers can access and generate outpatient medical records, patients' informed consent (ICF), EDC, and original medical records in the HIS system.

Laboratory inspectors and researchers can access and produce their own report forms of test results.

Data managers can access and generate data management data; statistical analysts can access and generate statistical analysis data.

The access and editing rights of the rest of the source data shall be specified in detail by the SOP of the corresponding departments in accordance with the requirements of the relevant laws, regulations, and technical specifications of China.

10、Finance and Insurance

The key researchers will make a written agreement and submit it to the relevant departments of their clinical research institutions for review, which will specify in detail the financial situation and payment method of this clinical trial. For details, please see the agreement signed.

11、Content covered by the clinical trial report

The main researchers organize statistical professionals to complete the statistical analysis report and complete the clinical trial summary report according to the contents

of the statistical analysis report. The statistical analysis report should at least include the general situation of clinical trials, clinical general data, safety and effectiveness data sets, the incidence and treatment of adverse events, and the description of program deviation, together with the original cases of the patients.

The clinical trial report should be consistent with the clinical trial scheme, and the contents should include:

- (1) General information;
- (2) Abstract;
- (3) Introduction;
- (4) Clinical trial purpose;
- (5) Clinical trial method;
- (6) Clinical trial content;
- (7) General clinical information;
- (8) Control diagnosis and treatment methods;
- (9) Statistical analysis methods and evaluation methods;
- (10) Clinical evaluation criteria;
- (11) Organizational structure of clinical trial;
- (12) Ethical explanation;
- (13) Clinical trial results;
- (14) Adverse events found in clinical trials and their management;
- (15) Analysis and discussion of clinical trial results, especially indications, scope of application, contraindications and matters needing attention;
- (16) Conclusion of clinical trial;
- (17) Existing problems and suggestions for improvement;
- (18) List of trial personnel;
- (19) Other circumstances to be explained;

12、Principle of confidentiality

This agreement and the contents of this clinical trial and all ancillary materials are confidential and belong exclusively to the team of researchers, and all researchers participating in the project shall be held confidential. The patent application, research process, and unpublished data shall not be disclosed to any third party except with the consent of the research team. This obligation of confidentiality shall remain valid after the termination of this trial.

13、Responsibilities of the researcher

- (1) Provide hospital supervision department with the trial scheme, EDC, informed consent form, etc;
- (2) Pre-trial training for clinical trial researchers;

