Before the start of the clinical trial, the person in charge of the trial center trains the researchers participating in the clinical trial, so that the researchers can understand and be familiar with the whole trial process and related operations.

4.4) Standard implementation of including and excluding standards

The patients are screened according to the inclusion and exclusion criteria of the trial scheme to reduce the selective bias.

4.5) Monitoring of clinical trials

Key researchers formulate monitoring plans and appoint independent inspectors to conduct regular on-site monitoring visits to experimental hospitals to ensure that all contents of the research program are strictly observed, and regularly check the database to ensure consistency with the contents of the original materials.

4.6) Blind evaluation

The centralized film reading is blinded, and the image is blinded by the statisticians to prevent the central film reviewers from knowing the subject's disease diagnosis, subject number and other information which can cause bias.

5) . Patients selection criteria

5.1) Inclusion criteria

- 1) Male patients with clinically suspected prostate cancer (abnormal digital rectal examination or serum PSA);
- 2) Finish the detection of serum PSA and multi-parameter magnetic resonance imaging (mpMRI);
- 3) $4 \text{ ng/ml} \leq \text{serum PSA} < 100 \text{ ng/ml}$;
- 4) Prediction threshold of csPCa evaluated by the model (online system) ≥ 0.60 ;
- 5) Finish 18F-PSMA-1007 PET/CT and present positive result;
- 6) Patients without contraindications of radical prostatectomy.

5.2) Exclusion criteria

- 1) Unable to perform PSA test or mpMRI examination;
- 2) Serum PSA $< 4 \text{ ng/ml}$ or $\geq 100 \text{ ng/ml}$;
- 3) Prediction threshold of csPCa evaluated by the model (online system) < 0.60 ;
- 4) Finish 18F-PSMA-1007 PET/CT but negative result;
- 5) Patients who have negative results in the previous prostate biopsy.
- 6) Patients refuse radical prostatectomy or still choose prostate biopsy.

6). Effectiveness evaluation

6.1) Definition

- 1) **True positive:** The diagnosis results of PSMA combined model and pathological examination are both csPCa.

2) False positive: The diagnosis result of PSMA combined with model is csPCa, while the pathological examination is not.

6.2) Main effectiveness index

Positive predictive value

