Definition: The patients with positive results of PSMA combined model and pathological examination accounted for the proportion of all patients with positive results of PSMA combined model.

Calculation method: Positive predictive value= $\frac{\text{true positive}}{\text{true positive}+\text{false positive}} \times 100\%$

6.3) Secondary effectiveness index

1) Misdiagnosis rate

Definition: The patients with positive results of PSMA combined model and negative results of pathological examination accounted for all patients with positive results of PSMA combined model.

Calculation method: Misdiagnosis rate= $\frac{\text{false positive}}{\text{true negative}+\text{false positive}} \times 100\%$

7. Safety evaluation

The severity, quantity and incidence of AE, ADR, and SAE and their correlation with overall trial, examination or operation and individual patients are statistically and descriptively analyzed.

(2) Study flow

1). Study flow chart

[figure not shown]

Table 1 The schedule of the screening period, perioperative period, and evaluation period for this trial.

Items	Screening period (-7~0 days)	Perioperative period of radical prostatectomy (1- 14 days)	Evaluation period
Demographic data	▲		
Signs and symptoms	▲		
Completed the blood test ^a and mpMRI examination	▲		
Evaluation by the online diagnostic model	▲		
Signing of informed consent forms	▲		
¹⁸ F-PSMA-1007 PET/CT examination ^b	▲		
Enrollment	▲		
Radical prostatectomy ^c		▲	

Reading of pathological slices			▲
Follow up and adverse events	▲	▲	▲

^a Prostate cancer marker test (Serum total PSA).

^b The researchers decide whether an ¹⁸F-PSMA-1007 PET/CT examination is performed based on the results of the risk probability by online diagnostic model evaluation.

^c The researchers decide whether the radical prostatectomy is performed based on the decisions of the patients and their relatives. Full preoperative communication is needed.

mpMRI, multi-parameter magnetic resonance imaging; ¹⁸F-PSMA-1007 PET/CT, ¹⁸F-prostate-specific membrane antigen-1007 positron emission tomography/computed tomography; PSA, prostate specific antigen.

2). Screening period (-7~0 day)

The following process will be completed during the screening period:

- Allocation of patient's number;
- Collection of demographic information (age, place of origin, height, weight, and healthy condition, etc.);

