- Collection of medical history information (allergic history, medical history, surgical history, family history of disease);
- Acquisition of signs and symptoms;
- Blood test of PSA and mpMRI examination;
- ¹⁸F-PSMA-1007 PET/CT examination;
- Acquisition the risk probability of csPCa by online dynamic nomogram;
- Review of inclusion / exclusion criteria
- Obtain the indication radical prostatectomy

The risk of csPCa is assessed by clinical predictive model (an online system). The prostate volume is calculated according to the maximum anteroposterior diameter, transverse diameter, and longitudinal diameter of prostate from mpMRI images. PSAD is the ratio of serum total PSA to prostate volume. The result of prostate mpMRI is quantified by PI-RADS (version 2.1). The range of scores is 1-5. The online dynamic nomogram is used to quantitatively evaluate the risk probability of patients, and the patients whose risk threshold reach 0.60 are defined as the positive patients of the

diagnostic model, and the 18F-PSMA-1007 PET/CT examination will be further completed and evaluated.

3). Perioperative period of radical prostatectomy (1~14 day)

The following procedures will be completed during the perioperative period of radical prostatectomy:

- Enrollment of patients;
- Signing of informed consent forms;
- Radical prostatectomy and get prostate specimen;
- AEs records

4). Evaluation period

4.1) Evaluation of the diagnostic results of PSMA combined model

Patients with risk probability ≥ 0.60 after assessing by the online dynamic nomogram. Meanwhile, further 18F-PSMA-1007 PET/CT examination also indicate the diagnosis of csPCa, that is, the patients have positive results by PSMA combined with model.

4.2) Reading of pathological slices

We set up blindness for reading of pathological slices. Three senior pathological physicians are randomly selected to form slices reading group as evaluators. The statisticians blind the pathological specimens, and the reading group interprets and analyzes the pathological specimens subsequently. Finally, a consensus is obtained.

The qualification requirements for senior pathologists are as follows:

- 1) A tertiary hospital doctor with GCP qualification;
- 2) Clinicians with 5 or more years of experience in reading pathological images of prostate cancer;
- 3) Do not participate in the screening process of patients.

3、 Statistical analysis

(1) Statistical design, methods, and analysis

1). Sample size

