This study is designed for a single group of objective performance criteria. With reference to the opinions of many senior clinical experts and statistical experts, it is considered that the clinically acceptable positive predictive value should not be less than 90%. According to the literature exploration and previous research results, it is expected that the positive predictive value of PSMA combined model is more than 98%. Suppose the significance level is 0.05 (bilateral) and the degree of power is 80%. The required number of positive samples (positive results in PSMA combined model) is 55. Considering the drop rate of 5%, the study is expected to enroll 57 patients.

2). Statistical analysis set

- 1) Full analysis set (FAS): the set of patients determined according to the intention to treat, which refers to the data set of all patients who participated in this study.
- 2) Per protocol set (PPS): refers to the completed trial and excludes patients who seriously violate the scheme (patients violate the selection criteria or exclusion criteria, etc.).
- 3) Security data set (SS): all the patients who participated in this study and conducted at least once safety assessment constitute the security population of this study.

3). Principle of statistical analysis

- 1) IBM SPSS (version 25.0) statistical software is used for statistical analysis.
- 2) All statistical tests use two-sided tests, and a P value of less than 0.05 will be considered to be statistically significant normally.
- 3) Description statistics: the measurement of continuous variables is described by means, standard deviation, and median, interquartile range; categorical variables are described by number and proportion (%).
- 4) The comparison of the two groups of variables will be analyzed by appropriate methods according to the type of variables. T-test or Wilcoxon rank sum test is used to compare measurement indexes between groups. χ^2 test or Fisher exact test is used to compare categorical variables between groups.

4). Group completion status

The selection and completion of the cases are described respectively, and the corresponding statistical analysis of the population is summarized and listed by the enrollment, drop, elimination, completed cases, and the number of cases of each analysis set.

5). Equilibrium analysis of baseline data

Baseline analysis based on full data set (FAS)

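### Table 1 places informed consent before the PET/CT that decides eligibility; the study-flow text places it after, in the perioperative period

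*Combined protocol and SAP*

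**What the plan says.** Three parts of the protocol bear on when consent is signed.

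- **Section 2(2), Table 1.** The screening column (days -7 to 0) carries marks, in row order, for evaluation by the online model, "Signing of informed consent forms", PET/CT and enrolment. Footnote b says the researchers decide on the scan "based on the results of the risk probability by online diagnostic model evaluation".
- **Section 2(2), text.** The screening list opens "The following process will be completed during the screening period" and includes PET/CT. It has no consent step and no enrolment step. The perioperative list (days 1 to 14) contains "Enrollment of patients" and "Signing of informed consent forms", followed by surgery.
- **Section 7(3).** "Only after the patients fully understand the experiment and sign the informed consent form can they be selected". PET/CT is not mentioned.

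Inclusion criterion 5 (section 2(1), 5.1) makes the scan an entry condition: "Finish 18F-PSMA-1007 PET/CT and present positive result".

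**The concern.** The table and the text are both current instructions for the same trial, and they put consent on opposite sides of the scan. The scan is a trial procedure: it is half of the combined model under test, the researchers trigger it, and its result decides whether a man can enter. If a site works from the text, men receive a radiotracer for trial purposes before they have agreed to take part. A man whose scan is negative then meets exclusion criterion 4 and leaves before the period in which consent is listed, so on that route he would not sign at all. At stake are the protection of participants and the validity of consent for the scan.

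**Working it through.** No calculation applies, and the plan states no figure on this point. The check is to set the passages side by side.

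| Step | Table 1 | Text of section 2(2) |
|---|---|---|
| PET/CT | Screening, days -7 to 0 | Screening, days -7 to 0 |
| Consent | Screening, row above PET/CT | Perioperative, days 1 to 14 |
| Enrolment | Screening, row below PET/CT | Perioperative, days 1 to 14 |

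**Step 1: is the consent conflict real?** Yes. It rests on the period headings. PET/CT falls in days -7 to 0 in both places, while consent falls in days -7 to 0 in one and days 1 to 14 in the other. In the text, consent therefore comes after the scan by at least the change of period.

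**Step 2: how much depends on list order?** Little. Bullet order in the text is not reliable: the screening list puts PET/CT above the nomogram result that triggers it. For the same reason, little should be made of the perioperative list naming enrolment above consent, although that order is the reverse of section 7(3). In Table 1, consent and PET/CT share a column, so their relative order there does rest on row order. That order (model, consent, scan, enrolment) agrees with footnote b and with inclusion criterion 5.

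**Step 3: does another section settle it?** No. Section 7(3) fixes consent before selection. Selection needs a positive scan, so the rule is satisfied whether consent comes before or after PET/CT. Section 7(1) likewise speaks only of consent before a subject enrols.

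**Step 4: is enrolment in conflict in the same way?** No. Enrolment follows PET/CT in both places, as inclusion criterion 5 requires. Only its period label differs: screening in Table 1, perioperative in the text.

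**Step 5: does the primary measure move?** Positive predictive value is true positives over true plus false positives (section 2(1), 6.2), or A/(A+B) in Table 2 of section 3(1). Section 3(1), 6.1 describes the denominator as the enrolled men. A man with a negative scan is negative on the combined model and belongs in row C/D, outside A+B. A man who is positive but chooses biopsy meets exclusion criterion 6 and is not enrolled. Neither enters the denominator under either schedule.

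**The case against.** The strongest defence is that Table 1 already schedules consent in screening, that section 7 requires a signature before entry, and that the perioperative entry could be a separate surgical consent. The flow chart and the consent pages are not available for review and might make this clear. Part of this stands: nothing shows that any man would in fact be scanned without consent, since a site may follow Table 1. But the perioperative item carries the same label as the Table 1 row and nothing identifies it as surgical. The text also has no other consent step, and no further document can make these two passages agree.

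Three stronger readings are tempting, and the documents do not support them.

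- **A reader might infer that Table 1 enrols men before PET/CT.** It does not; the enrolment row comes after the scan.
- **A reader might infer that the full analysis set has two memberships.** The set is defined by participation, "which refers to the data set of all patients who participated in this study", and not by the date of consent. Membership would clearly change with the schedule only if participating meant having consented, which no passage says. That word is loose, and the protocol summary speaks of model-negative men as in the study while section 2(1) excludes them. That looseness exists whatever the timing of consent.
- **A reader might infer that the primary denominator could grow and the trial fail.** Counting two men without surgery as failures would lower the exact (Clopper-Pearson) 95% lower limit from 93.7% for 57/57 to 88.3% for 57/59, below the 90% target. But no passage counts such men as failures, and Step 5 shows that they fall outside the denominator.

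**Conclusion.** The timing of consent is wrong as written and should be corrected. Table 1 and the section 2(2) text cannot both be followed, and under the text the PET/CT that decides eligibility precedes trial consent. The enrolment discrepancy is minor, being one of period label only.

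The conflict touches every man who has the trial scan. That is at least the 57 men planned for enrolment, plus those scanned and found negative, whose number the documents do not state. How many would be scanned before consent depends on which passage a site follows and cannot be estimated. No effect on the primary estimate, its confidence interval or the sample size is claimed.

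The conclusion assumes that the consent named in both places is the trial consent, as the identical label suggests.

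**What to change.** Reconcile Table 1 with the text of section 2(2):

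1. In the text, move trial consent from the perioperative list to the screening list, after the online model result and before PET/CT, as in Table 1.
2. Give enrolment the same period in Table 1 and the text, after consent and a positive PET/CT.
3. If the perioperative form is a separate consent to surgery, label it so and keep it there as an additional item.
4. In section 7(3), add that trial consent precedes PET/CT, so that all three places agree.

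The cost is a wording amendment. The downside is that some men will consent and then be screened out because the scan is negative or because they choose biopsy. Sections 3(1), 4) and 5) already provide for reporting enrolment and excluded cases, so little extra reporting is needed.

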power is 80%. The required number of positive samples (positive results in PSMA combined model) is 55. Considering the drop rate of 5%, the study is expected to enroll 57 patients.

The negative samples are all the patients in the study who are negative in the PSMA combined model and should perform prostate biopsy.

Analysis set

- 1) Full analysis set (FAS): the set of patients determined according to the intention to treat, which refers to the data set of all patients who participated in this study.
- 2) Per protocol set (PPS): refers to the completed trial and excludes patients who seriously violate the scheme (patients violate the selection criteria or exclusion criteria, etc.).
- 3) Security data set (SS): all the patients who participated in this study and conducted at least once safety assessment constitute the security population of this study.

Primary endpoint analysis

The primary endpoint of this study is the positive predictive value of PSMA combined model for the diagnosis of csPCa. For the analysis of the primary endpoints, the results of both FAS and PPS will be taken into account. The positive predictive value of PSMA combined model for csPCa diagnosis and its 95% confidence interval (95%CI) will be recorded. When the lower limit of 95%CI is greater than the target value, it is considered that the detection rate of PSMA combined model is up to the standard, which can be used as a proof for a new clinical treatment scheme called biopsy-free radical prostatectomy.

Secondary endpoint analysis

	
No target value is set for the secondary endpoint, and only the detection rate and 95%CI are calculated at the time of evaluation.
 
Safety endpoint analysis
 
The severity, quantity and incidence of AE, ADR and SAE and their correlation with overall trial, examination or operation and patients are statistically and descriptively analyzed.

Expected duration	12 months

1、Background

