The number of patients enrolled in the group, the number of completions, and the total drop rate are described respectively, and the list of excluded cases and the detailed list of unfinished reasons are listed. The baseline features of the patients are statistically described.

6). Evaluation indexes

The analysis of effectiveness indexes is based on the full analysis set (FAS) and the per-protocol set (PPS) and is described in the table below.

Table 2 Statistical analysis of main indicators ^f

		Results of pathological diagnosis		total
		positive	negative	
PSMA combined model	positive	A	B	A+B
	negative	C	D	C+D
		total	A+C	B+D
				N=A+B+C+D

Positive predictive value (true positive rate)= $A/(A+B) \times 100\%$;

Misdiagnosis rate= $B/(A+B) \times 100\%$.

6.1) Main effectiveness indexes

The most important effectiveness index of this study is the positive predictive value (true positive rate) of PSMA combined model, which is the proportion of the positive results of postoperative pathological diagnosis to all enrolled patients. For the analysis of the primary endpoint, the results of both FAS and PPS will be considered. The positive predictive value of PSMA combined model for csPCa diagnosis and its 95%

CI will be calculated, when the lower limit of 95%CI is greater than the set target value, it is considered that the detection rate of PSMA combined model is up to the standard, which can be used as a proof for a new clinical treatment scheme called biopsy-free radical prostatectomy.

6.2) Secondary effectiveness evaluation index

The secondary endpoint of the study is the detection rate of any-grade PCa (Gleason score $\geq 3+3$) and high grade PCa (hgPCa) (Gleason score $\geq 4+3$) by PSMA combined model, the positive predictive value and misdiagnosis rate of any-grade PCa and hgPCa will be assessed.

Notably, no target value is set for the secondary endpoint indexes, and only the point estimated value and 95% CI are calculated at the time of evaluation.

Safety endpoint analysis

6.3) Safety evaluation

The severity, quantity and incidence of AE, ADR and SAE and their correlation with overall trial, examination or operation and patients are statistically and descriptively analyzed. In addition to the above statistical methods, detailed and additional exploratory analysis may be required and confirmed in the Statistical Analysis Program (SAP).

3、Data management

(1) Raw data verification

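### With two-sided 0.05 held, 55 evaluable patients give about 70% power at a PPV of 98%, not 80%, and the unnamed confidence interval decides the verdict at 1 or 2 false positives

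*Combined protocol and SAP*

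**What the plan says.** The sample-size text appears in the Protocol summary (Sample size estimation) and in section 3, Statistical analysis, (1) 1) Sample size, with the same inputs in both places:

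- Target: "it is considered that the clinically acceptable positive predictive value should not be less than 90"%.
- Expectation: "it is expected that the positive predictive value of PSMA combined model is more than 98"%.
- Error and power: "Suppose the significance level is 0.05 (bilateral) and the degree of power is 80"%.
- Result: "The required number of positive samples (positive results in PSMA combined model) is 55".
- Allowance for loss: "Considering the drop rate of 5%, the study is expected to enroll 57 patients".

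The success rule is in the Protocol summary (Primary endpoint analysis), "When the lower limit of 95%CI is greater than the target value", and in section 3 (1) 6.1) Main effectiveness indexes, "when the lower limit of 95%CI is greater than the set target value". Neither place says how the interval is computed. The principles of analysis in section 3 (1) 3) name SPSS 25.0 and two-sided testing at 0.05, and nothing more on this point. No sample-size formula or software is given.

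**The concern.** The primary outcome is a count of false positives among about 55 specimens, so only a handful of decision rules exist. Moving the cut-off by one specimen changes power and error by large steps. Two things follow.

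- A power claim at this sample size has to match one of those rules, and 80% matches none that keeps the stated error.
- When the interval is not named, the cut-off is not named either, so the primary result is not fully defined before the data are seen.

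The plan says that meeting the criterion would serve as proof for biopsy-free prostatectomy, and it names removal of a tumour-free prostate as the main risk. A rule under which 2 false positives in 55 can be a pass or a fail is weak support for such a claim.

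**Working it through.** **Inputs (all from the sample-size and primary-analysis text).** Target PPV p0 = 0.90; expected PPV p1 = 0.98, taken as the floor of the stated expectation; two-sided 0.05, so 0.025 in the success direction; power 80%; n = 55 evaluable; 57 enrolled.

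**Step 1: try to reproduce 55.** The usual one-sample formula is n = [z(α)·√(p0(1−p0)) + z(β)·√(p1(1−p1))]² / (p1−p0)². Two-sided, this is (1.960×0.3 + 0.842×0.14)² / 0.08² = 77.8, so 78. Other methods with the same inputs:

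| Method | Two-sided | One-sided |
|---|---|---|
| Score formula | 78 | 59 |
| Score with continuity correction | 90 | 71 |
| Arcsine | 61 | 48 |
| Variance at p1 only | 25 | 19 |
| Variance at p0 only | 111 | 87 |
| Exact test, smallest n with power ≥ 80% | 70 | 61 |

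None comes within 2 of 55. The documents do not say how 55 was obtained, and I make no claim about its origin.

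**Step 2: exact properties of each cut-off at n = 55.** With X the number of false positives, the upper-tail error is P(X ≤ c) at PPV 90% and power is P(X ≤ c) at PPV 98%.

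- P(X=0 | 0.98) = 0.98^55 = 0.3292
- P(X=1 | 0.98) = 55×0.02×0.98^54 = 0.3695
- P(X=2 | 0.98) = 1485×0.02²×0.98^53 = 0.2036

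| False positives allowed | Upper-tail error at 90% | Power at 98% |
|---|---|---|
| 0 | 0.3% | 32.9% |
| 1 | 2.2% | 69.9% |
| 2 | 7.7% | 90.2% |

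Only the first two rows keep the error within 2.5%. The third also exceeds 5%, so reading the 0.05 as one-sided does not rescue it.

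**Step 3: which cut-off does the written rule imply?** Lower 95% limits at n = 55:

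| Interval | 54/55 | 53/55 | False positives allowed |
|---|---|---|---|
| Clopper-Pearson | 90.3% | 87.5% | 1 |
| Wilson | 90.4% | 87.7% | 1 |
| Jeffreys | 91.8% | 88.8% | 1 |
| Wald | 94.7% | 91.4% | 2 |
| Agresti-Coull | 89.5% | 87.0% | 0 |

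As a check on the Wald entry: 53/55 = 0.9636, and 0.9636 − 1.96×√(0.9636×0.0364/55) = 0.914. With 3 false positives even Wald fails (88.5%).

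**Step 4: how often the choice matters.** At a true PPV of 98%, Wald disagrees with the other four at exactly 2 false positives, probability 20.4%. Agresti-Coull disagrees with the other four at exactly 1, probability 36.9%. The sum is 57.3%.

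**Step 5: sensitivity with at most 1 false positive, n = 55.**

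| True PPV | 96% | 97% | 98% | 98.5% | 99% |
|---|---|---|---|---|---|
| Power | 34.9% | 50.6% | 69.9% | 80.0% | 89.5% |

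At PPV 98%, power is 70.6%, 69.1% and 68.4% for n = 54, 56 and 57, with upper-tail errors of 2.4%, 2.0% and 1.8%. At n = 53 Clopper-Pearson allows no false positive (52/53 has a lower limit of 89.9%), and power drops to 34.3%. If each of 57 patients is lost independently with probability 5% (my assumption), 4 or more are lost with probability 31.8%.

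**The case against.** **The expectation is above 98%, so 98% is the worst case.** True: a PPV of 98.5% or 99% also satisfies the wording and gives at least 80%. But a sample size has to deliver its power at the value stated, and 98.5% appears nowhere in the plan. This softens the shortfall and does not remove it.

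**The 57.3% leans on Agresti-Coull.** This is fair. At 54/55 the other four intervals agree, and nothing suggests that Agresti-Coull would be used. Without it, the disagreement is Wald against the rest at exactly 2 false positives: about one trial in five, with power of 70% or 90%.

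**A later analysis plan may name the interval.** The data-management section has the analyst follow a statistical analysis plan, so the gap could be closed before database lock. However, section 3 (1) 6.3) leaves to that plan only further detailed and exploratory analysis. The primary criterion is set in the present text, without a method.

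**Low power cannot cause a false endorsement.** Correct. The power statement is a matter of honest disclosure. The unnamed interval carries the greater weight, because Wald would let a model with a PPV of exactly 90% pass 7.7% of the time.

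**The 53-patient case is peripheral.** The plan's own 5% leaves about 54 of 57 (57×0.95 = 54.2), where power is 70.6%. Still, one patient fewer removes the only false positive allowed, so it should be stated.

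**Conclusion.** The concern holds. With 55 evaluable patients and the stated two-sided 0.05 kept, the design has 69.9% power at a PPV of 98%. That is 10.1 points below the stated 80%: the criterion is missed about 3 times in 10 rather than 2 in 10. The result is the same for Clopper-Pearson, Wilson and Jeffreys, since all three allow exactly 1 false positive.

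Separately, the success rule is undetermined as written. Power at 98% is 32.9%, 69.9% or 90.2% depending on the interval, and under Wald the upper-tail error is about three times nominal (7.7/2.5 = 3.1). The choice decides 20.4% of trials at a PPV of 98% if only Wald is in dispute, and 57.3% if Agresti-Coull is admitted as well.

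These figures assume independent binomial outcomes, a target of 90%, 2.5% error in the success direction, and 98% as the planning value.

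**What to change.** Change the wording in four places; no extra patients are needed.

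1. In the Protocol summary (Primary endpoint analysis) and in section 3 (1) 6.1), write: *The 95% CI is the two-sided Clopper-Pearson interval. With 54 to 57 evaluable patients the criterion is met with at most 1 specimen that is not csPCa; with 53 evaluable, none is allowed.*
2. In both sample-size paragraphs, replace the 80% power statement with: *With 55 evaluable patients, exact power is about 70% at a true PPV of 98% (80% at 98.5%, 51% at 97%; 34% at 98% if only 53 are evaluable); the one-sided type I error is at most 2.5%.*

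The same text should define an evaluable patient and say whether the FAS or the PPS decides, because the cut-off depends on the denominator.

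The cost is a less favourable stated power and the loss of freedom to choose the interval later. If the sponsor prefers to keep 80% at a PPV of 98%, exact two-sided power first reaches it at 70 evaluable patients (83.5%) and stays at or above it from 85.
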